1.8. Power, Sample Size, with Estimation of Missing Subjects Follow-up

The primary Veteran outcomes are SAPS and SANS, and family outcome is caregiver burden. Note, for these outcome measures higher scores indicate worse symptoms. The equivalence ratio that will be tested is the mean of DSW/mean of in-person MFG. For both Veterans and family members we plan for the study to detect equivalence ratios of 1.2 for the two measures of psychotic symptoms (SAPS and SANS) and caregiver burden. In these hypotheses tests the null hypotheses are that DSW outcome means are inferior to MFG. The ‘alternative’ hypotheses are that outcomes means in the DSW arm are equivalent to outcomes in the in-person MFG arm. If as an example, the symptoms are higher in the DSW arm, and thus the ratio of the mean of the DSW arm to the mean of the in-person MFG arm exceeds 1.2 (i.e. mean of DSW > mean in-person MFG by 20% or more) we will accept the null hypothesis that the mean of DSW > mean of in-person MFG, and that DSW is not as effective as in-person MFG. Any ratio of DSW/MFG that is < 1.2 will cause us to reject the null hypothesis and accept the alternative that they are equivalent. For the caregiver burden scale the equivalence ratio that leads to rejection is slightly smaller, it is 1.17 because there is only 1 primary measure. With 42 subjects per treatment arm, power is >80% with one tailed alpha =0.025 to detect equivalence ratios of 1.2 (and above). For testing whether DSW is superior to in-person MFG on the illness symptom measures we can reverse the ratio and test whether (mean of in-person MFG/mean DSW) is > 1.20. For these sample size calculation we used reported data to estimate the coefficients of variation (CV) of the scales. CVs commonly range from 0.3-0.5 and within this range there were differences in the calculated equivalence ratios. For alpha =0.025, and CV equal to 0.3 the equivalence ratio bound was 1.20 with an increase to 1.29 for a CV of 0.5.

For the in-person MFG arm a correction for nesting of subjects in a group is needed, which increases the number of subjects required. If it is assumed that this dependency is 0.01 and groups are of size 6-8 then variance inflation factor is on the order of 10%, resulting in 46-47 subjects being needed for the in-person MFG arm. Because DSW is available separately for each Veteran and family member it is not necessary to increase the 42 subjects needed for this group. The

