1.7. Data Analysis

Overview. Initially we will assess whether our stratified randomization procedures yielded groups equivalent in groups on the stratification factors and other demographic and clinical variables. These analyses will be completed with chi-square statistics for categorical variables (or Fisher Exact statistics as needed for small ns) and t-tests for continuous measures (or Kruskal-Wallace tests if there are serious deviations from normality on these variables). Our initial analyses of the primary dependent measures for Veterans, the SAPS and SANS, and for family members/supporters, Caregiver Burden, will test the mean ratios at time points 12 and 15 months to test for non-inferiority. Then the analyses will be move to mixed effect regressions with the primary effects of interest the interaction between time of measurement and treatment group. The use of mixed effect regression allows us to include subjects with partially complete data, e.g. missing the 6 month interview but have baseline, and 12 month interview data available (see below). Prior to the regression analyses we will also check to insure that the continuous measures (SAPS, SANS, Caregiver Burden) are normally distributed. If these assumptions are violated we will identify appropriate transformations to normalize these outcomes or use different forms of the outcome variables and regression techniques that do not require normality to be appropriate. Also of interest will be differences between completers vs. non-completers across the 2 groups as well as within groups (see specifics below under Aims 1 and 2).

1.7.1. Specific Aim 1

We will conduct a 2-arm, non-inferiority randomized comparative effectiveness trial of DSW and in-person multi-family MFG. We will compare changes in severity of Veterans' of psychiatric symptoms (i.e., positive and negative symptoms), and caregiver psychological burden, during the treatment period and then 3-months post-treatment.

Hypothesis 1.1. Veterans participating in DSW will do as well or better than those participating in in person MFG with an equivalence ratio of 1.20-1.47 (depending on the coefficients of variance of the measures assessed) at time points 12 and 15 months.

Hypothesis 1.2. Family caregivers participating in DSW will do as well as or better than those participating in in-person MFG with an equivalence ratio of 1.17-1.29 (depending the coefficient of variance of the measure assessed) at time points 12 and 15 months.

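### The non-inferiority margin is not fixed: Section 1.8 decides at 1.2 but also gives 1.17 and 1.29, and Hypotheses 1.1 and 1.2 give CV-dependent ranges reaching 1.47 and 1.29

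*Combined protocol and SAP*

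**What the plan says.** All references are to the combined protocol and SAP. Higher scores are worse, and Section 1.8 defines the comparison: "The equivalence ratio that will be tested is the mean of DSW/mean of in-person MFG".

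**SAPS and SANS**
- Section 1.8, decision rule: "Any ratio of DSW/MFG that is < 1.2 will cause us to reject the null hypothesis".
- Section 1.8, sample size, at alpha 0.025 and starting from CV 0.3: "the equivalence ratio bound was 1.20 with an increase to 1.29 for a CV of 0.5".
- Section 1.7.1, Hypothesis 1.1: as well or better "with an equivalence ratio of 1.20-1.47 (depending on the coefficients of variance of the measures assessed) at time points 12 and 15 months".

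**Caregiver burden**
- Section 1.8, planning statement: "we plan for the study to detect equivalence ratios of 1.2 for the two measures of psychotic symptoms (SAPS and SANS) and caregiver burden".
- Section 1.8, a few sentences later, on the ratio leading to rejection: "slightly smaller, it is 1.17 because there is only 1 primary measure".
- Section 1.7.1, Hypothesis 1.2: "equivalence ratio of 1.17-1.29 (depending the coefficient of variance of the measure assessed").

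On the source of the CVs, Section 1.8 says that for sample size "we used reported data to estimate the coefficients of variation (CV) of the scales" and that they commonly lie between 0.3 and 0.5. Section 1.7.1 does not say whether the CV in the hypotheses is this planning value or the one observed in the trial. No section gives a reason, in terms of acceptable loss of effect relative to MFG, for any of the ratios.

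**The concern.** A non-inferiority trial needs one margin per primary outcome, set in advance, because the margin decides the conclusion. Here the Veteran outcomes have 1.2, 1.29 and 1.47 as candidate upper values, and caregiver burden has 1.17, 1.2 and 1.29. The 1.47 appears only in Hypothesis 1.1 and exceeds every bound in Section 1.8.

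A margin that depends on the CV raises two further problems. First, the noisier the scale, the larger the deficit that counts as non-inferior; this is how a detectable difference at fixed sample size behaves, not a tolerable loss. Second, because the plan does not tie the margin to a planning CV, choosing it after the data are seen is not excluded. The same data could then support opposite conclusions.

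**Working it through.** **Inputs from Section 1.8:** 42 per arm, one-sided alpha 0.025, power above 80%, CV 0.3 to 0.5, margins as quoted. **Assumed, because the plan names only PASS 2008:** log-normal outcomes, t-test on the log scale, true ratio 1 for power, no nesting correction. Non-inferiority is declared when the upper confidence limit lies below the margin M.

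**Formulas.** σ = √ln(1 + CV²); SE = σ√(2/42); df = 82; t(0.975) = 1.989. Power comes from the noncentral t with noncentrality ln(M / true ratio) / SE.

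| CV | σ | SE |
|---|---|---|
| 0.3 | 0.294 | 0.0641 |
| 0.4 | 0.385 | 0.0841 |
| 0.5 | 0.472 | 0.1031 |
| 0.7 | 0.632 | 0.1378 |

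**Step 1: reproduce the plan's base case.** With M = 1.20 and CV 0.3, noncentrality is 0.1823 / 0.0641 = 2.85 and power is 80.3%. This agrees with the stated 42 per arm and supports the assumed method.

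**Step 2: where the ranges come from.** Ratio detectable with 80% power at 42 per arm:

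| CV | one-sided 0.025 | one-sided 0.05 |
|---|---|---|
| 0.3 | 1.199 | 1.174 |
| 0.4 | 1.269 | 1.235 |
| 0.5 | 1.339 | 1.295 |
| 0.7 | 1.478 | 1.413 |

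The range 1.20–1.47 matches the 0.025 column from CV 0.3 to about 0.7; 1.47 itself needs CV 0.69, outside the stated 0.3–0.5. The range 1.17–1.29 matches the 0.05 column from CV 0.3 to 0.5. Section 1.8 labels 1.29 at CV 0.5 as an alpha 0.025 figure, but this method gives 1.34 there. At 0.025, 1.29 corresponds to CV 0.43; at 0.05, to CV 0.49. By inference, the ranges in the hypotheses are power outputs.

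**Step 3: can the choice reverse a conclusion?** At CV 0.5 and an observed ratio of 1.00, the upper 97.5% limit is exp(1.989 × 0.1031) = 1.228. That fails 1.20 and passes 1.29. The largest observed ratio that passes is M × exp(−1.989 × SE):
- M 1.20, CV 0.3: 1.20 / 1.136 = 1.056
- M 1.20, CV 0.5: 1.20 / 1.228 = 0.978
- M 1.29, CV 0.5: 1.29 / 1.228 = 1.051

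Between the two pairs documented in Section 1.8 (1.20 at CV 0.3, 1.29 at CV 0.5) the passing ratio hardly moves, 1.056 against 1.051. The loosening is relative to a fixed 1.2.

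**Step 4: chance of declaring non-inferiority when DSW is truly 20% worse** (true ratio 1.20):

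| M | CV | noncentrality | probability |
|---|---|---|---|
| 1.20 | 0.5 | 0 | 2.5% |
| 1.29 | 0.5 | 0.0723 / 0.1031 = 0.70 | 10.3% |
| 1.47 | 0.7 (assumed) | 0.2029 / 0.1378 = 1.47 | 30.7% |
| 1.47 | 0.5 (illustrative) | 0.2029 / 0.1031 = 1.97 | 49.4% |

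Simulation with 200,000 runs gave 2.5%, 10.1% and 30.7% for the first three rows. The documents attach no CV to 1.47, so the last two rows are conditional.

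**Step 5: power once the margin is fixed** (true ratio 1, 42 per arm):

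| Margin, one-sided alpha | CV 0.3 | CV 0.4 | CV 0.5 |
|---|---|---|---|
| 1.20, 0.025 | 80% | 57% | 42% |
| 1.17, 0.025 | 68% | 45% | 32% |
| 1.17, 0.05 | 78% | 58% | 45% |

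By the normal approximation, 80% power at M = 1.20 and one-sided 0.025 needs 41, 71 and 106 per arm at these CVs, before nesting and attrition.

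**The case against.** The strongest defence is that Section 1.8 does contain an operative rule: 1.2 in general, with 1.17 as a specific exception for caregiver burden. On that reading the 1.2 for burden belongs to a planning sentence, and the ranges in the hypotheses are mislabelled detectable ratios, so no margin was ever meant to move with the observed CV. This may be what the authors intended, and no passage says that an observed CV would set the margin. But the formal hypotheses still state the ranges, burden still carries two values in one section, and a reader cannot tell from the text which governs.

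Three objections to the numbers deserve weight.
- The 1.29 at CV 0.5 may really be a one-sided 0.05 figure. The matching upper limit for an observed 1.00 is then exp(1.664 × 0.1031) = 1.19, which passes both 1.20 and 1.29, so that example depends on the alpha of 0.025 that Section 1.8 states.
- The plan words its rule on the ratio itself and mentions no confidence limit. Taken literally, an observed 1.00 passes every margin. Even so, at true ratio 1.20 and CV 0.5 the declaration rate is 50% with 1.20 and Φ(0.70) = 76% with 1.29, so the choice of margin still matters.
- The finding that 1.29 does not reproduce depends on method. A difference-scale calculation gives 1.31 at CV 0.5, which is closer, but 1.18 at CV 0.3, which fits the stated 1.20 less well.

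It is also fair that justifying a margin clinically is a separate task from reconciling the numbers; both are needed here.

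**Conclusion.** The concern holds and must be fixed. The textual conflict is certain: three candidate values for each primary outcome, with the hypotheses tied to an unspecified CV and nothing to say which value decides. The quantified consequences are conditional on the log-scale confidence-limit test, 42 per arm and one-sided 0.025. On that basis, moving from 1.20 to the documented 1.29 at CV 0.5 raises the chance of accepting a truly 20% worse DSW about fourfold (2.5% to 10%). With 1.47 it would be about 31%, if the CV is near 0.7. That the ranges are detectable ratios carried into the hypotheses is an inference, though the reproduction in both alpha columns supports it strongly.

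**What to change.** - State one margin per primary outcome, identically in Sections 1.7.1 and 1.8, fixed before outcome data are analysed and independent of the CV.
- Have the sponsor justify each margin as a tolerable loss of effect relative to MFG. The existing rule already supplies 1.2 for SAPS and SANS, but 1.20 and 1.17 also coincide with detectable ratios at CV 0.3, so they need that justification too.
- Reconcile 1.2 and 1.17 for caregiver burden. If 1.17 reflects a different alpha because there is only one measure, state that as the alpha, not as the margin.
- Delete both ranges from the hypotheses. Report CV-dependent values only in the power section, labelled as detectable ratios with their CV and alpha, and correct or explain the 1.29.

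The text change is a short amendment plus a margin justification. The real cost is that the power statement must be rewritten: at a fixed 1.2, 42 per arm gives about 80% only at CV 0.3 and falls to 42% at CV 0.5. The sponsor would have to accept that openly, support a CV near 0.3, or enlarge the trial.

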A standard question will be asked of the Veteran to identify the person who is their primary family supporter or other primary support person. To verify this, a similar question will be asked of the support person identified. If there is a tie between two or more support persons (e.g., family members), it will be the person who spends the most face-to-face time with the Veteran who will be used as the “primary” support person for data collection.

Recruitment of Family/Support persons

To recruit family members and support persons, the Veteran will be asked to identify appropriate persons (family, other support persons). A brochure explaining the study will be sent to such persons, either by mail or the Veteran will provide it to him or her. Staff will also tell family about the study when they see them at a clinic, or talk with them as part of standard clinical care over the telephone. Family and support persons will be provided with a number and contact information of a study recruited, who they can get in touch with for additional information concerning the study. If they are interested in participating they will be formally consented to join the study by research staff. The primary support person/family member for the veteran must be ≥ 18 years old and able to speak and read English at the 5th grade level.

1. After consenting, and then baseline data collection, participants will be assigned to one of two treatment arms. Those in each arm will receive a different form of multi-family psychoeducation treatment. One arm will receive Multi-

Family Group (MFG). This treatment is provided in in-person group meetings that occur every other week for one year. The other arm will receive the treatment for one year via the Daily Support Website.

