b. Daily Support Website (DSW). Participants assigned to be in the Daily Support Website arm will receive access to this website and its associated functionalities. The DSW provides the following five resources. (1) Three on-line group forums. One for persons with SZ/SZA only (the SZ/SZA peer group), one for family/supporters only, and a combined group for both persons with SZ/SZA and support persons. In each group the therapists emphasized discussions that focus on problem-solving, alleviating stresses, and encouraging peer interactions. (2) Educational materials and tutorials. (3) A section to ask questions and receive an answer from the therapists associated with the project. (4) A library of previously asked and answered questions. (5) A list of community resources. Those who do not have a computer will have a computer (e.g., laptop, touch pad, or chrome book) provided to them, and Internet service, both free of charge to allow them to participate in the intervention. After their participation is over they will return the equipment.

The DSW treatment begins with two participant engagement activities. The first activity is joining sessions where the study therapist(s) meets with each individual participant (veteran, and when present supporter). These meetings can be in-person, via phone or over the internet. The purposes of the meetings are to develop a collaborative relationship, discuss the DSW, facilitate comfort with the e-health approach to receiving treatment, and develop an individual goal or identify a current 'issue' or 'complaint' that is bothering the individual. These meetings can involve both individual participant meetings as well as joint family meetings (i.e., veteran and his/her family/supporters). The number of meetings varies by

individual and family need (as jointly determined by the therapist and the participants). During the initial treatment period a therapist or research staff member may call a participant to ensure there are no issues with accessing the DSW, such as problems with equipment or lack of understanding of one or more aspects of using the DSW.

2. Participant Data collection. Outcomes data will be collected at scheduled time points of baseline (0), 6, 12, and 15 months. Each of these sessions is estimated to take about 2 hours. The data to be collected is described in Table 4.1.

Table 1.1. Data collection

Information	Measure

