Hypotheses 1.3. When compared to in-person MFG, Veterans and family members receiving DSW will have higher treatment initiation, engagement, attendance, lower drop-out, and higher perceived social support.

1.7.2. Specific Aim 2

We will conduct exploratory analyses to identify Veteran and family characteristics that are associated with severity of psychiatric symptoms and caregiver burden across both treatment arms. Analyses will look for important moderators (e.g. baseline symptom level, distance from hospital, age, technology expertise) as well as mediators (e.g., in-person meeting attendance, amount of DSW usage).

These analyses will be completed by supplementing the mixed effect regressions with demographic (age, race education), pre-study computer experience, support (living situation) and clinical characteristics (symptom severity, severity of cognitive impairment) of subjects that affect the relationships between the treatment and outcomes. Analyses will be carried out across both arms and then for each arm separately. While it is possible to test the treatment X non-treatment moderators with interaction terms the number of subjects precludes analyses that include all factors and interactions.

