Mediating effects of the different intervention components and different patterns of attendance and engagement are likely to occur in this study and will also be identified with mixed effect regressions. To test for mediating effects we will compare the relationships between treatment and outcomes and these potential mediating variables and outcomes. We assume that exposure, i.e., increased numbers of in-person session attendance, or more usage of DSW, will lead to greater improvements. These will help us to identify whether it is the amount of time spent on the materials/in treatment, or the duration of time one is exposed to treatment. Those in DSW and in-person MFG could have up to 1 year exposure, but usage patterns will identify the actual period of time over which Veterans were actually exposed to MFG materials, and the amount of time they used those materials. Thus, though the duration is the same in both treatments, the actual amount of exposure is not necessarily the same in both. For these analyses with 80 subjects in a multivariable regression with treatment included the detectable R^2 difference of an additional variable is 0.06 with 3 added variables it is 0.09 and with as many as 8 additional variables (or degrees of freedom) the detectable difference in R^2 is 0.12 (alpha=0.05, power=80%). The usual rule of thumb is to include at most $n/(8-10)$ variables in a multivariable regression, thus the analyses will be limited to 8 variables including the treatment variable.

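### Aim 2: each named mediator exists in only one arm, so a pooled model that uses it cannot show what carries a DSW-versus-MFG difference

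*Combined protocol and SAP*

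**What the plan says.** All references are to the combined protocol and SAP.

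- **Mediators.** Section 1.7.2, labelled exploratory, lists "mediators (e.g., in-person meeting attendance, amount of DSW usage".
- **Analysis sets.** In the same section, in the paragraph on participant characteristics: "Analyses will be carried out across both arms and then for each arm separately".
- **Method.** The mediation paragraph says: "To test for mediating effects we will compare the relationships between treatment and outcomes and these potential mediating variables and outcomes". Its power sentence assumes 80 subjects with treatment in the regression.
- **Expected direction.** "We assume that exposure, i.e., increased numbers of in-person session attendance, or more usage of DSW, will lead to greater improvements".
- **Who can have which exposure.** Section 1.0 on DSW: "Participants assigned to be in the Daily Support Website arm will receive access to this website and its associated functionalities". On MFG: "This treatment is provided in in-person group meetings that occur every other week for one year". The preliminary joining sessions of the DSW arm are an exception to a clean split: "These meetings can be in-person, via phone or over the internet".
- **Measures that exist in both arms.** Item 1.1.14 defines weeks attended for each treatment: a DSW week counts if the participant was logged on for at least 15 minutes, and each MFG meeting counts as two weeks. Table 1.1 also lists participant treatment contact time, from staff logs and server logs. No section says that either of these is the exposure in the pooled mediation analysis.

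**The concern.** To explain a difference between two treatments, a mediator has to be something that either treatment could raise or lower. DSW usage is structurally zero for everyone in MFG, and bi-weekly group attendance is structurally zero for everyone in DSW. Assignment alone decides whether the exposure can occur, so the treatment-to-mediator path is fixed by design and carries no information.

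Adding such a variable still changes the treatment coefficient, and that change is easily read as the mediated part with the remainder as the direct part. A paper could then report that attendance or website use accounts for a DSW-versus-MFG difference, or masks one, when the analysis shows only a dose-response inside one arm. Aim 2 is meant to separate amount from duration of exposure, and this would answer a different question.

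**Working it through.** **1. The plan's own figure.** Section 1.7.2 gives detectable R² increments of 0.06, 0.09 and 0.12 for 1, 3 and 8 added variables (80 subjects, alpha 0.05, power 80%). With a noncentral F test, noncentrality f²·N and treatment as the one base predictor, the required f² is 0.1006, 0.1436 and 0.2092. The increment is f²(1 − R²base)/(1 + f²). At an assumed base R² of 0.30, which the plan does not state:

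- 0.1006 × 0.70 / 1.1006 = 0.064
- 0.1436 × 0.70 / 1.1436 = 0.088
- 0.2092 × 0.70 / 1.2092 = 0.121

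These round to the stated values (at base R² = 0 they would be 0.091, 0.126 and 0.173). The point does not rest on them. They matter here because the calculation describes a pooled model with treatment in it.

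**2. What the pooled model can be.** A treatment–outcome relationship can be estimated only with both arms present. If an arm-specific exposure is entered, the other arm is coded either zero or missing. If missing, that arm drops out and treatment cannot be estimated. If zero, step 3 applies.

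**3. Algebra (one time point, T = 1 for DSW, T = 0 for MFG).** Regress the outcome on T and attendance A, with A = 0 throughout DSW. The T term absorbs the DSW mean, so the slope b of A is fitted from MFG alone. The T coefficient is then

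mean(DSW) − [mean(MFG) − b·mean(A in MFG)],

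that is, all of DSW against MFG extrapolated to no attendance. It differs from the unadjusted coefficient by b × mean(A). With DSW usage U entered instead, slope c, the shift is −c × mean(U). In simulation the pooled and within-arm slopes agreed to less than 1e-15.

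**4. Numbers.** Assumed, not in the documents: both arms have mean outcome 30; MFG attendance averages 15.6 of 26 sessions; DSW use averages 40 hours; residual SD 9. Arm sizes 47 and 42 are from section 1.8. The true arm difference is 0.

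| Slopes (per session / per hour) | T with attendance | T with usage |
|---|---|---|
| 0 / 0 | 0 | 0 |
| −0.15 / −0.05 | −0.15 × 15.6 = −2.34 | +0.05 × 40 = +2.0 |
| −0.3 / −0.1 | −0.3 × 15.6 = −4.68 | +0.1 × 40 = +4.0 |
| −0.6 / −0.2 | −0.6 × 15.6 = −9.36 | +0.2 × 40 = +8.0 |

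As the total is 0, the apparent mediated effect is the same size with the opposite sign. Separate simulations of the third row gave −4.4 to −4.8 and +4.0 to +4.1. In one set of 4,000 trials, the treatment term was significant at 5% in 4.6% of trials unadjusted, 19% with attendance and 30% with usage.

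**5. An exposure with no causal effect.** Assumed: weeks attended with mean 26, SD 12, limited to 0–52; outcome SD about 1; an unmeasured factor correlated r with attendance and −r with outcome. The slope is about −r²/12, so the false indirect effect is about −26r²/12.

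| r | Formula | Simulated mean | Significant |
|---|---|---|---|
| 0 | 0 | 0.00 SD | about 5% |
| 0.3 | −0.195 SD | −0.20 SD | 9% |
| 0.5 | −0.542 SD | −0.56 SD | 36% |

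**6. The shared scale.** With weeks attended measured in both arms, and equal average attendance, the indirect effect was significant in at most 0.8% of runs in every scenario, because the treatment-to-exposure path is then truly zero and can be estimated as such. The exposure–outcome slope itself was still significant in 62–66% of runs at r = 0.5, so this confounding remains.

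**7. What is lost by not pooling the named variables.** For the slope, almost nothing: at r = 0.5 it was significant in 35.8% of pooled runs and 36.3% of within-arm runs. The figure of 0.06 does not carry over to a single arm, however. At base R² 0.30, the detectable increment for one variable is 0.1963 × 0.70 / 1.1963 = 0.115 with 42 subjects and 0.1744 × 0.70 / 1.1744 = 0.104 with 47.

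**The case against.** A reader might infer that the pooled analysis manufactures effects out of nothing. The documents do not support that. The plan has treatment in the model, and then an inert, unconfounded exposure leaves the treatment coefficient unchanged and the error rate near 5%. An inert exposure gave frequent false signals (50% of runs, with a true arm difference of 0.5 SD) only when treatment was left out, which is not what the plan describes. Nor does the shift depend on units: 40 hours × 0.1 and 2,400 minutes × 0.1/60 are both 4.0. In the third row of the table in step 4, the −4.68 and +4.0 follow from dose effects that were put in; MFG members who never attended really would score worse in that scenario.

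Other points on that side also stand:

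- The plan does not say that exposure is coded zero in the other arm, or that mediation is read from the change in the treatment coefficient.
- The sentence about analysing both arms sits in the paragraph on participant characteristics, and the two mediators are given as examples.
- Separate-arm analyses are already planned, and the mediation paragraph speaks of amount and duration of exposure in both arms.
- Joining sessions can be in person in DSW, so the structural zero applies to group sessions and website use, not to every in-person contact.
- Aim 2 is exploratory.

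These limit the harm but do not remove the problem. Comparing mediators with the treatment effect needs both arms, the only mediators named are arm-specific, and no shared measure is assigned to that analysis. The sponsor also expects a dose-response, so a zero slope is not the planning assumption.

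**Conclusion.** The point holds as one of interpretation. With the named mediators, the pooled analysis returns a within-arm slope and a treatment contrast at zero exposure in one arm. It cannot say how much of a DSW-versus-MFG difference passes through a common exposure pathway. Where there is a dose-response, real or confounded, two arms with equal means will show direct and mediated effects of opposite sign, and those signs reverse according to which arm's exposure is entered.

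The size is slope times mean exposure. The documents give neither, so the −4.7 and +4.0 points are illustrations, and the range runs from zero upwards with the slopes. The algebra is for a linear model at one time point without covariates; with baseline covariates or repeated measures, the equality of pooled and within-arm slopes becomes approximate, but the structural zeros stay. No primary hypothesis is affected.

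**What to change.** Amend section 1.7.2 as follows.

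1. For any pooled mediation analysis, name an exposure defined in both arms: weeks attended as in item 1.1.14, or participant treatment contact time from Table 1.1. Include treatment, an arm-by-exposure term and baseline covariates, and state the exposure value at which the treatment contrast is read.
2. Report group-session attendance and DSW usage only in the separate-arm analyses, as baseline-adjusted dose-response associations, and do not call them mediation of the treatment effect.
3. Label the pooled result associational. A shared scale makes the treatment-to-exposure path estimable but leaves the exposure–outcome slope open to confounding. Weeks attended also equates the arms by convention (one meeting counts as two weeks, and 15 minutes online as one), so contact time is a useful sensitivity analysis.

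No new data are needed. Treatment, exposure and their interaction use 3 of the 8 variables the plan allows, which leaves 5 for baseline covariates. The remaining cost is a little more analysis work and the larger detectable increments within each arm (0.104 to 0.115 at the assumed base R² of 0.30), which should be stated beside the pooled figure.

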42 and 47 subjects per treatment arm respectively (n=89 total) represent the number of Veterans that need to complete their assigned interventions. We expect that the non-completion rate for the in-person MFG arm to be $\leq 33\%$ and DSW arm to be $\leq 10\%$. Given these estimates 70 in person MFG subjects will be enrolled and 47 DSW subjects, for a total of 117 to account for attrition and non-completers. Sample size calculations used PASS (2008, NCSS, LLC, Kaysville Utah.).

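### Aim 2 looks for moderators of the treatment effect but commits to no treatment-by-moderator interaction test, only to pooled and separate per-arm fits

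*Combined protocol and SAP*

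**What the plan says.** Section 1.7.2 states the status of the aim: "We will conduct exploratory analyses to identify Veteran and family characteristics" associated with symptom severity and caregiver burden. It then names moderators (four examples: baseline symptoms, distance from hospital, age, technology expertise) and mediators (meeting attendance, amount of DSW use). The next paragraph adds demographic, computer-experience, support and clinical covariates to the mixed regressions, as factors that alter the relation between treatment and outcome.

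The method is one sentence: "Analyses will be carried out across both arms and then for each arm separately". The sentence after it opens "While it is possible to test the treatment X non-treatment moderators with interaction terms" and closes "the number of subjects precludes analyses that include all factors and interactions".

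The section gives no list of interactions to be tested, no one-at-a-time plan, no count of tests, and no rule for reading the arm-specific fits. Its power figures concern added variables in a pooled regression: "with 80 subjects in a multivariable regression with treatment included the detectable R^2 difference of an additional variable is 0.06", and "with 3 added variables it is 0.09". None concerns an interaction or a within-arm fit.

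**The concern.** A moderator is a factor whose relation to outcome differs between the arms. A pooled main effect shows prognosis averaged over arms, and a within-arm slope shows association in that arm. Neither compares the two slopes. With no interaction test specified, the natural way to use two per-arm fits is to note which factors reach significance in one arm and not in the other. In arms of this size, that contrast can arise by chance when the slopes are identical. At stake are exploratory statements about which Veterans or families do better with DSW or with MFG, which could guide later targeting of the two formats.

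**Working it through.** **Inputs.** Arm sizes are from section 1.8: "42 and 47 subjects per treatment arm respectively (n=89 total) represent the number of Veterans that need to complete their assigned interventions" (DSW 42, MFG 47). Two-sided alpha of 0.05 and the regression n of 80 are from section 1.7.2. The documents give no within-arm R², so a range is assumed.

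**1. The plan's own power figures.** For n = 80, alpha 0.05, 80% power and treatment as the one base variable, use the noncentral F test with f² = ΔR²/(1 − R²_base − ΔR²) and noncentrality n·f². The stated 0.06, 0.09 and 0.12 (1, 3 and 8 added variables) come out as 0.064, 0.088 and 0.121 if the base R² is about 0.30. With base R² of 0 they would be 0.091, 0.126 and 0.173. So they can be reproduced under an unstated assumption, but they describe pooled power only.

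**2. Same slope in both arms, significance compared between arms.** Within-arm power p is from the F test on 1 and n − 2 df with noncentrality n·R²/(1 − R²). The arms are independent, so P(significant in exactly one arm) = p₁(1 − p₂) + p₂(1 − p₁).

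Example at R² = 0.06: 0.06/0.94 = 0.0638, so the noncentralities are 42 × 0.0638 = 2.68 and 47 × 0.0638 = 3.00. The powers are 0.359 and 0.396. Then 0.359 × 0.604 + 0.396 × 0.641 = 0.47. For an unrelated factor: 2 × 0.05 × 0.95 = 0.095.

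| Assumed within-arm R² | Power, n=42 | Power, n=47 | Significant in exactly one arm | Same, simulated | Interaction test, simulated |
|---|---|---|---|---|---|
| 0 | 5% | 5% | 9.5% | 9% | 4.8% |
| 0.02 | 15% | 16% | 26% | 26% | 5.1% |
| 0.06 | 36% | 40% | 47% | 46% | 4.8% |
| 0.10 | 56% | 61% | 49% | 49% | 4.9% |
| 0.15 | 76% | 81% | 34% | 36% | 5.0% |
| 0.20 | 89% | 92% | 18% | 21% | 4.9% |
| 0.30 | 99% | 99% | 2% | 4% | 5.1% |

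The simulations used 20,000 trials per row. The calculated peak is 50%, near R² = 0.08. With 40 per arm the pattern is similar.

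**3. Several candidates.** For four factors treated as independent, the chance of at least one discordant result is 1 − (1 − 0.095)⁴ = 33% if all are unrelated to outcome, and 1 − (1 − 0.471)⁴ = 92% if all have R² of 0.06. Four interaction tests give 1 − 0.95⁴ = 19%.

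**4. Does sample size favour per-arm fits?** With k factors and time left aside, a pooled model with every factor interacted with treatment has 2k + 2 coefficients (intercept, treatment, k main effects, k products). Two per-arm models have 2(k + 1) = 2k + 2, the same number. One interaction at a time needs treatment, moderator and their product, which is 3 variables and inside the plan's limit of 8. That limit rests on n = 80. The plan's n/(8-10) rule allows 42/10 to 42/8, or 4.2 to 5.3, variables in the DSW arm, and 47/10 to 47/8, or 4.7 to 5.9, in the MFG arm.

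**5. Power of the alternative.** At a single time point, with a standardised moderator, the slope difference detectable with 80% power is (1.96 + 0.84) × √(1/42 + 1/47) = 2.80 × 0.212 = 0.59 residual SD per SD of moderator. Simulated power is 28% at 0.3, 45% at 0.4, 62% at 0.5 and 77% at 0.6.

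**The case against.** A reader might infer that the plan replaces interaction tests with per-arm significance, and so will often report false moderators. The text does not support this. It says interactions can be tested and excludes only a model with all factors and interactions together, which leaves room for a limited set. Nowhere does it say that significance in one arm only will be called moderation, so the 26-50% is the error rate of a likely use and not of a stated rule.

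Per-arm fits also have proper uses. Part of Aim 2 is prognostic, and DSW use and MFG attendance are arm-specific exposures that have to be modelled within their own arm.

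The size depends on covariate strength. Discordance is rare at R² of 0.30, a level that baseline symptoms may reach. The 5% for an interaction test is per test: four moderators on three primary outcomes make 12 tests, and if these were independent the chance of a false positive would be 1 − 0.95¹² = 46%. Most such tests would also have little power.

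All of this stands, and it limits the point. It does not supply the missing piece: possible is not planned, and nothing the section commits to compares slopes between arms.

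**Conclusion.** The point holds as a gap in an exploratory aim: moderators are sought and no test of moderation is committed to. The discordance rates in the table apply only if arm-specific significance is compared. They assume equal true slopes, one time point, completer numbers and within-arm R² values that the documents do not give. The planned mixed models with repeated visits would change the exact figures. They would not change the fact that two separate significance tests do not test a difference between slopes. The sample-size remark is sound against one model with everything in it. It gives no reason to prefer per-arm fits to single interactions. The change is worth making because it is nearly free, but the non-inferiority tests on SAPS, SANS and caregiver burden do not depend on it.

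**What to change.** In section 1.7.2, state that:

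- a short list of candidate moderators, drawn from the factors the section already names, is fixed before analysis;
- each is tested one at a time with a moderator-by-treatment term (and its product with time) in the pooled mixed model;
- each estimate is reported with its confidence interval as exploratory, with the number of tests made;
- arm-specific moderator estimates are descriptive only;
- within-arm fits are kept for arm-specific exposures such as DSW use and MFG attendance.

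The cost is SAP wording, with the same data and model family. The drawback is the low power shown in step 5. Wide confidence intervals will make that visible.
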